At the second study call, participants ($N=608$) will be randomized to one level of each of 4 factors (see Table 2): 1) Medication Type (Varenicline vs. C-NRT), 2) Preparation Medication (4 weeks vs. Standard), 3) Medication Duration (Extended vs. Standard), and 4) Counseling (Intensive vs. Minimal). Participants will complete phone assessments one week pre-quit, during the first week post-target quit date (TQD) and at Weeks 2, 4, 12, 20, 26, and 52 post-TQD.

Assessments

Call 1. At Call 1, participants will complete the phone screen, complete the oral consent and HIPAA authorization process, and complete a brief demographics assessment. After this call, participants will be mailed a Study Information Sheet that contains all of the information related to the study. They will also be sent information on how to use WebEx so they can have video visits if they so choose.

Call 2. Participants will answer questions about their smoking and other tobacco use history, their self-efficacy and motivation, their physical and emotional health, the impact of Covid-19 on their life and their beliefs about Covid-19 and smoking, and their satisfaction with their health care and they will complete the Fagerström Test of Cigarette Dependence¹¹⁷ (see Table 1). Participants will be randomized to their treatment condition, set a target quit date, and be educated about their assigned medication (including how and when to request refills).

Calls 3-6. Participants will receive a call one week pre-quit, during the first week post-target quit date (TQD) and at Weeks 2 and 4 from their Health Counselor. This research staff member will assess: a daily smoking calendar using timeline follow-back¹¹⁸, medication use (as appropriate

PROTOCOL
 "P01 Cessation Screening Study"
 PI: [name].; UW-CTRI Grant:

based on study condition), use of alternative nicotine products (e.g., e-cigarettes), withdrawal, self-efficacy, and adverse events. We will recommend dosage/use alterations as per good clinical practice if participants experience adverse events. Participants will be referred to their primary care physician should they require medical consultation. Participants will also receive smoking cessation counseling as appropriate, based on their assigned treatment condition. If the call does not include treatment it will not be conducted by the participant's health counselor (i.e., Calls 5 and 6 for those in the Minimal Counseling condition).

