Primary Aim 2: To identify two optimized smoking cessation treatments: one for varenicline and one for C-NRT. Data on both the 12-month abstinence effect sizes and costs of the different intervention components and combinations of components will be examined and multiple criteria decision analysis will be used to determine how to use each medication so that it is highly effective and but low in cost.

Secondary Aims: To determine: 1) whether person factors (e.g., sex, dependence, psychiatric history) moderate response to different treatment strategies; and 2) which proximal effects of each treatment factor mediate its long-term benefits; and 3) the main and interactive effects of the cessation interventions on cost-effectiveness and the cost-effectiveness of the optimal combinations of components for each medication type.

Implementation Challenges: Pandemic and Varenicline

Study recruitment began in November 2020.

In June 2021 Pfizer found that some lots of varenicline contained elevated levels of a novel nitrosamine that exceeded the level thought to be safe by the FDA for traditional nitrosamines. Therefore, we briefly paused recruitment. When we resumed recruitment, all participants were randomized to the C-NRT level of the Medication Type factor until November 2021 when we received IRB approval to use FDA-approved generic varenicline. When we were able to procure FDA approved varenicline, we changed our randomization ratio on this factor to 2:1 varenicline to C-NRT. When FDA initiated the varenicline recall, there were 42 participants actively taking

varenicline; 26 participants opted to switch to C-NRT and 16 stopped all medication. These 42 participants will not be included in the main outcome analyses.

We experienced significant implementation challenges with collecting in-person breath samples for biochemical verification of abstinence. In September 2023 we transitioned from using exhaled CO to verify abstinence ($\text{CO} < 6\text{ppm}$) to using cotinine assays on mailed saliva samples to verify abstinence ($\text{cotinine} \leq 10\text{ng/mL}$).

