The question of primary interest is how treatments affect abstinence amongst diverse smokers amidst the variety of other factors that also influence smokers' ability to maintain abstinence, not whether such effects occur in a statistically adjusted sample. Therefore, the primary analyses will first be conducted without covariate adjustment, to ensure that covariate adjustment does not cloud interpretation or reduce external validity for various reasons. In secondary analyses, we will statistically control for covariates including: living with a smoker, biological sex, age, clinic, health system, use of other tobacco products at baseline, cigarettes per day at baseline,

and education. In addition, primary analyses will exclude participants who were switched to cNRT from varenicline or stopped using any medication during the FDA varenicline recall.

Self-reported point-prevalence abstinence at Weeks 12 and 26 and biochemically confirmed abstinence at Week 26 will be analyzed as secondary outcomes using methods similar to those used for the primary outcome. These analyses will allow us to examine the stability or robustness of the intervention component effects.

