The robustness of the optimized treatments will then be evaluated with regard to other factors such as patient preference and implementation/burden data (e.g., required clinician/staff time). We will conduct sensitivity analyses that vary both the criteria and weightings (derived from stakeholder data) to examine the robustness of the identified optimized care packages.

Secondary Aims Analyses. Analysis of moderators of abstinence outcomes will use regression tree analyses that can identify differential treatment responses in 6- and 12-month abstinence. Candidate moderators of treatment effects on abstinence will include: living with a smoker, biological sex, age, use of other tobacco products at baseline, cigarettes per day at baseline, and education, and psychiatric history. Candidate mediators of cessation treatment effects will be: medication use and side effects, attendance at counseling sessions, withdrawal symptoms (e.g., craving, negative affect, anhedonia), and cessation self-efficacy. Treatment effects will be modeled as main effects and 2-way interactions with the outcomes being 6- and 12-month biochemically confirmed 7-day point-prevalence abstinence. Mediation analyses will use bootstrapped confidence intervals of the mediated effect. Care will be taken to preserve mediator/outcome temporal priority and the occurrence of smoking during the quit attempt will be statistically controlled. Mediation models will include multiple mediators and will use methods developed for use with dynamic mediator assessments (maximum likelihood estimation using hierarchical linear modeling: HLM 5.04).

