Additional Analyses. We will examine the main and interactive effects of the 4 factors on the occurrence of adverse events and treatment engagement (count and proportion of counseling sessions completed [1 session for Minimal vs. 4 sessions for Intensive], counseling modality [video vs. phone] chosen for remote protocol participants, count and proportion of medication refills requested [1 for Standard Duration vs. 3 for Extended duration]). Logistic and linear regression will be used for categorical and continuous variables, respectively, with appropriate transformations of continuous variables and/or adoption of generalized regression modeling techniques as necessary. The primary analyses will be unadjusted and then we will statistically control for covariates including: living with a smoker, biological sex, age, clinic, health system, use of other tobacco products at baseline, cigarettes per day at baseline, and education. Analyses of these exploratory outcomes will achieve scientific rigor by controlling for experiment-wise error in families of related tests using the Benjamini-Hochberg approach.

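### The SAP names no baseline covariate for its mediation models, so confounding of the non-randomised mediator-to-abstinence path can distort the mediated effects under Secondary Aim 2

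*SAP*

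**What the plan says.** The SAP's Study Overview makes mediation part of the secondary aims: to determine "which proximal effects of each treatment factor mediate its long-term benefits". The protocol's own list of secondary aims omits mediation, although its overview mentions potential mediators.

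The mediation plan is in the SAP under Secondary Aims Analyses:

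- Mediators: "Candidate mediators of cessation treatment effects will be: medication use and side effects, attendance at counseling sessions, withdrawal symptoms", followed by cessation self-efficacy.
- Model terms and outcomes: "Treatment effects will be modeled as main effects and 2-way interactions with the outcomes being 6- and 12-month biochemically confirmed 7-day point-prevalence abstinence".
- Inference: "Mediation analyses will use bootstrapped confidence intervals of the mediated effect". Several mediators enter together, and hierarchical models handle repeated mediator assessments.
- Control: attention to the time order of mediator and outcome, and "the occurrence of smoking during the quit attempt will be statistically controlled".

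No baseline covariate is named. The SAP's two covariate lists belong elsewhere. One is under Primary Aim 1 ("In secondary analyses, we will statistically control for covariates including: living with a smoker, biological sex, age, clinic, health system"). The other, under Additional Analyses, concerns adverse events and treatment engagement ("The primary analyses will be unadjusted and then we will statistically control for covariates including: living with a smoker, biological sex, age, clinic"). Both lists include cigarettes per day. Neither includes a dependence score, motivation, self-efficacy, baseline withdrawal or psychiatric history.

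At Call 2 the protocol collects "their self-efficacy and motivation, their physical and emotional health" and the Fagerström dependence score.

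**The concern.** Each factor is randomised, so its effect on a mediator is protected from confounding. The mediators themselves are not randomised: withdrawal, self-efficacy, medication use and session attendance are states and behaviours of the participant. A more dependent, less motivated or more distressed smoker may have worse withdrawal, use less medication and attend less, and may also be less likely to quit. Putting the mediator before the outcome in time does not remove a common cause that precedes both.

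The one named control does not fill the gap. Smoking during the quit attempt comes after randomisation and may itself be affected by both the factor and baseline dependence.

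At stake is the answer to SAP Secondary Aim 2. A proximal effect could be credited with a benefit that it does not produce, or a real mechanism could be missed.

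**Working it through.** **The plan's own figures.** The documents give no figure for mediation. The nearest stated figures are the main-effect powers in the protocol's Sample Size and Power Considerations (304 per level, α = .05). With two-sided α and pooled variance under the null, z = (|p₁−p₂| − 1.96·√(2p̄q̄/n)) / √(p₁q₁/n + p₂q₂/n).

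- 15% vs 25%: (0.10 − 1.96 × 0.03244) / 0.03219 = 1.131, power 0.871 (stated .87).
- 20% vs 30%: (0.10 − 1.96 × 0.03512) / 0.03489 = 0.893, power 0.814 (stated .81).

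Both reproduce, but they say nothing about mediation.

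**Inputs for the illustration.** From the SAP: 538 recruited, and 42 excluded from the main outcome analyses. If the 42 are among the 538 (assumed), 538 − 42 = 496. All else is assumed: about 19–20% abstinent (0.20 × 496 ≈ 99 participants), a factor that shifts the mediator by *a* SD, a mediator effect *b* on the log-odds of abstinence, and a baseline variable U that correlates *c* with the mediator and changes the log-odds by *g* per SD.

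**Size of the bias.** Within arms, mediator and U have unit variance and correlation *c*. Omitting U therefore shifts the mediator slope by about *g·c*, and the mediated effect *a·b* by about *a·g·c*. The last column comes from simulations of 1,000,000 subjects.

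| a | true b | c | g | true a·b | approximate unadjusted a·b | simulated unadjusted a·b |
|---|---|---|---|---|---|---|
| 0.3 | 0 | .2 | −.3 | 0 | 0.3 × (−0.06) = −0.018 | −0.018 |
| 0.3 | 0 | .4 | −.5 | 0 | 0.3 × (−0.20) = −0.060 | −0.058 |
| 0.3 | 0 | −.4 | −.5 | 0 | 0.3 × 0.20 = 0.060 | 0.057 |
| 0.3 | 0.3 | .4 | −.5 | 0.090 | 0.3 × (0.3 − 0.2) = 0.030 | 0.029 |
| 0.3 | 0.3 | −.4 | −.5 | 0.090 | 0.3 × (0.3 + 0.2) = 0.150 | 0.144 |
| 0 | 0 | .4 | −.5 | 0 | 0 | −0.001 (zero within simulation error) |

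The bias can thus create, mask or inflate mediation. It can also reverse it: with true b = 0.1 and a shift of −0.2, the slope becomes −0.1, and a·b becomes −0.03 instead of +0.03. With U in both equations the simulated product returned to its true value (0.000, or about 0.090).

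**False positives at n = 496, true b = 0.** The method was least squares for the mediator, logistic regression for abstinence, and a Monte Carlo 95% interval for a·b as a stand-in for the bootstrap. With a = 0.35 SD and U ranging from a weak confounder (about c = .2, g = −.3) to a strong one (about c = .4, g = −.5):

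| Model | weak | middle | strong |
|---|---|---|---|
| One mediator, no baseline term | 8% | 16% | 37% |
| Lapse variable also controlled | 6% | 10% | 24% |
| U in both equations | 3–6% | 3–6% | 3–6% |

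The second row also rests on assumed links between U, lapse and abstinence. A variant with two further mediators and lapse in the model, all driven by U, gave 7%, 11% and 23%.

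**When the factor does not move the mediator (a = 0).** The mediator slope is still biased, but the product stays at zero. The false-positive rate was 0.3% (c = .2, g = −.3) to 3.7% (c = .4, g = −.8).

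**Effect of the named control alone.** Suppose a = 0 and the factor and U both affect early smoking. Conditioning on that smoking without U makes the factor and U dependent. The estimated a then became 0.010 to 0.041 and a·b about −0.001 to −0.007. This is small, but not zero.

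**The case against.** A reader might infer that the plan has decided against baseline adjustment, and that baseline dependence will therefore show up as mediation. The documents support neither step.

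- The SAP is silent; it does not exclude covariates. The protocol's Inclusion/Exclusion section promises statistical control of psychiatric diagnoses, prior cessation medication and other tobacco use in unspecified analyses. This stands, but the promise does not reach dependence, motivation or baseline mediator levels.
- A baseline variable cannot by itself produce a mediated effect of a randomised factor; apart from the small effect of conditioning on later smoking, the factor must move the mediator. This stands too. The trial expects that condition to be met, however. The counseling arms differ in the sessions offered and the duration arms in the weeks of medication, while withdrawal suppression and enhanced self-efficacy are the SAP's own example mediators.
- Even under the strongest confounding in the main table, most simulated trials (63%) showed no false effect, and the weakest case is little above 5%.
- A one-mediator model is not the planned model. Controlling lapse cuts the excess, which is why both rows are shown. The hierarchical models might also use a pre-quit mediator level, though the SAP does not say so.
- Baseline withdrawal rests on Table 1 alone, which marks it at C1 and C2. The text for Calls 1 and 2 does not mention it. Table 1 also puts random assignment at C1, while the text puts it at Call 2. Call 3 cannot serve as baseline for the Preparation arms, which are already on medication by then.

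**Conclusion.** The point holds as a gap in specification with a real bias behind it. Run as written, the mediation models leave the mediator-to-abstinence path open to confounding by variables that the trial measures before treatment. Where a factor moves a mediator, the estimated mediated effect can be wrong in either direction.

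The size for this trial is not known. The ranges of about 8% to 37% (single mediator) and about 6% to 24% (lapse controlled), against about 5% after adjustment, rest entirely on assumed effect sizes, on 496 analysed participants and on roughly 20% abstinence. They show what is possible and are not a forecast.

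The consequence is confined to SAP Secondary Aim 2. The factor effects on abstinence do not depend on the mediation models, and the packages are chosen on abstinence and cost.

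**What to change.** In the SAP's Secondary Aims Analyses, state that both the mediator and the outcome equations include a small prespecified set of variables measured at Call 2 before treatment: the Fagerström dependence score, motivation, baseline self-efficacy, and emotional health or psychiatric history. Add baseline withdrawal once it is confirmed to be collected before treatment, as Table 1 shows. State the assumption of no unmeasured mediator-outcome confounding, and add a sensitivity analysis showing how strong such confounding would have to be to change each conclusion. Give the reason for controlling post-randomisation smoking, or drop that control.

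The cost is some SAP wording and a few more model terms; the Call 2 items need no new data. Precision falls slightly. With roughly 100 abstinent participants (assumed) and several mediators in the model, the covariate set must stay small, and it should be fixed before the mediation results are seen.

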Participants will be told their treatment condition at Call 2, set a target quit date (TQD), and instructed how to use their study medications. Medications will be mailed following this call, along with a handout that describes: 1) when to begin taking study medication; 2) the type and doses involved; 3) how and when to obtain the next month's medication; and 4) complete instructions on proper medication use, including information from the package insert and contact information if they have questions regarding their medication and/or symptoms they experience. Participants will be mailed all Preparation Medication as well as one month of post-quit study medication after Call 2. They will need to call in to a study line to request that more medication be mailed to them (Standard Duration participants will call one time to receive their final 2 months of medication; Extended Duration participants will call once to get 2 additional months of medication and again to get the remaining 3 months of study medication). Participants will also receive a counseling handout with their medications; those randomized to intensive counseling will receive a Quit Plan listing their target quit day and when they start the medications and those randomized to minimal counseling will receive the mHealth handout.

Medication Type: Varenicline vs. C-NRT. Half of participants will be assigned to receive varenicline and half to receive nicotine patch + mini-lozenge (C-NRT). Unless participants are assigned to Preparation or Extended Duration, they will receive the standard dosing and duration of pharmacotherapy (e.g., 12 weeks of varenicline starting 1 week prequit or 12 weeks of C-NRT starting on the TQD; see Table 2).

Preparation

Medication: 4 weeks vs. Standard. Half of participants will be assigned to receive the Preparation Medication ("ON" condition); they will be instructed to use their assigned medication type (varenicline or nicotine patch) for 4 weeks prior to their TQD (see Table 2). Participants will use a lower dose of NRT (14-mg patches) while they are still smoking to reduce the risk of adverse events. Our prior research found no significant increases in adverse events among smokers who used NRT prior to the TQD and prior research has shown that use of

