varenicline up to 35 days prior to the quit day is safe and effective. Participants assigned to the "OFF" level start their C-NRT use on their TQD or the standard Preparation varenicline, which starts 1-week pre-TQD (see Table 2).

Medication Duration: Extended vs. Standard. After Call 2, all participants will be mailed enough medication to get through the first month post-TQD and instructed to call a toll-free study number to have their refills mailed to them. Half of participants will be assigned to the Extended Duration (i.e., the "ON" condition); these participants will be able to use varenicline for 23 weeks post-TQD (24 weeks post-TQD if also randomized to preparation meds) or use C-NRT for 24 weeks post-TQD (see Table 2). The other half of participants will have varenicline for 11 weeks post-TQD (12 weeks post-TQD if also randomized to preparation meds) or C-NRT for 12 weeks post-TQD. We will urge all participants to use all of their study medication, regardless of whether they are abstinent or not.

Counseling: Intensive vs. Minimal. Half of the participants will be assigned to the Intensive Counseling condition and will receive four 15-20-minute counseling sessions occurring 1 week prequit, during the first week post-TQD and during Weeks 2 and 4 (see Table 1). During the first counseling call, the HC and participant will create a quit plan that the HC will then mail to the participant following the call. The counseling will be provided either via HIPAA-secure WebEx

Table 2. Medication Dosing

| | | Cessation Medication: Standard Duration (12 Weeks) | Cessation Medication: Extended Duration (24 Weeks) |
|-------------------------|------------------------|--|---|
| Varenicline | | 
No Preparation Meds:
 
 ▪ Days 1-3: 0.5 mg pill QD ▪ Days 4-7: 0.5 mg pill BID ▪ Day 8 (TQD)-Week 11: 1 mg pill BID 
Preparation Meds:
 
 ▪ Days 1-3: 0.5 mg pill QD ▪ Days 4-7: 0.5 mg pill BID ▪ Day 8-Week 16: 1 mg pill BID (TQD in Week 4) | 
No Preparation Meds:
 
 ▪ Days 1-3: 0.5 mg pill QD ▪ Days 4-7: 0.5 mg pill BID ▪ Day 8 (TQD)-Week 23: 1 mg pill BID 
Preparation Meds
 
 ▪ Days 1-3: 0.5 mg pill QD ▪ Days 4-7: 0.5 mg pill BID ▪ Day 8-Week 28: 1 mg pill BID (TQD in Week 4) |

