The other half of the participants receive a brief (15-30 minute) phone/video counseling session 1 week prior to the TQD to promote engagement with free mobile health (mHealth) resources: smokefree.gov and/or the Wisconsin Tobacco Quit Line, mHealth resources developed and maintained by the National Cancer Institute and the Wisconsin Department of Health Services. This will include a fax referral to the Wisconsin Tobacco Quit Line, which will then fax back to the research office what services the participant received (i.e., did they complete the counseling call, were they sent any smoking cessation medications). Smokefree.gov allows participants to develop a quit plan and access different quit smoking resources. The Quit Line is an interactive program that involves one-on-one telephone coaching sessions with a trained Quit Line coach to encourage smoking cessation, offer personalized advice on how to quit, information on medications, and assistance with choosing a quit date and creating a plan. This counseling will include informing participants about the features of the resources and encouraging them to sign up during their counseling session and a mailing that describes the mHealth resources. Participants will then receive a brief (10-20 minute) follow-up phone/video session during the first week post-TQD to mimic a nurse or clinician follow-up after a quit attempt and to provide additional mentoring around the use of the mHealth resources (e.g., has the participant signed up/used these resources, recommendation for specific pages that would be appropriate).

All participants will receive the medication conditions as outlined above, regardless of their counseling condition. Regular team meetings will discuss safety, confidentiality, and fidelity to the counseling manual. Health counselors (HCs) will also meet for 2 hours/month for clinical supervision with the Project Leader, [name], a licensed clinical psychologist, to review the study protocol and address treatment issues.

Promoting Continued Experimental Participation

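### The Counseling effect on session count and the Duration effect on refill count are built in by design, and the matching proportions move the other way if uptake declines over time

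*SAP*

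**What the plan says.** The SAP, Additional Analyses, sets out exploratory tests: "We will examine the main and interactive effects of the 4 factors on the occurrence of adverse events and treatment engagement (count and proportion of" and so on. The two measures at issue are "count and proportion of counseling sessions completed [1 session for Minimal vs. 4 sessions for Intensive" and "count and proportion of medication refills requested [1 for Standard Duration vs. 3 for Extended duration". Logistic, linear or generalized regression is planned, with Benjamini-Hochberg control within families of tests. No common time window, per-contact model or limit on which factors are tested on which measure is given.

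The Protocol, Interventions, describes what each level is offered:

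- **Refills.** Under Standard there is a single refill call, which supplies the last two months. Under the longer course there are two: "Extended Duration participants will call once to get 2 additional months of medication and again to get the remaining 3 months of study medication". The first mailing covers one month after the quit date and the first refill two more, so the second Extended request falls about three months after the quit date.
- **Sessions.** Intensive participants "will receive four 15-20-minute counseling sessions occurring 1 week prequit, during the first week post-TQD and during Weeks 2 and 4". For Minimal, "The other half of the participants receive a brief (15-30 minute) phone/video counseling session 1 week prior to the TQD", followed by one further session in the first week after the quit date. Table 1 shows the same pattern.

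The SAP, Secondary Aims Analyses, also lists candidate mediators, among them "medication use and side effects, attendance at counseling sessions, withdrawal symptoms".

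**The concern.** For two factor-outcome pairs, Counseling on sessions and Duration on refills, the factor under test sets the maximum score and the period over which it is earned. A test of no difference in count is then a test of a hypothesis that is false by construction. The proportion removes the difference in maximum but not the difference in timing, because the extra contacts all come later.

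The two versions of one outcome could therefore be reported as significant in opposite directions, with no difference in behaviour at any contact that both levels have. A reader could take the count as evidence that Extended medication or Intensive counseling raises engagement, or the proportion as evidence that it lowers it. Benjamini-Hochberg adjustment does not protect against this, because the expected difference itself is shifted. If attendance enters the mediation models as a total count, it would largely restate Counseling assignment.

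**Working it through.** **The plan's own figures.** None is given for engagement. The only design calculation is power for abstinence with 304 per level: .87 for 15% vs 25% and .81 for 20% vs 30%. A two-sided .05 test gives 0.871 and 0.814, so the same test is used below.

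**Inputs.** Contacts offered, from the Protocol: refill calls 1 (Standard) vs 2 (Extended); sessions 2 (Minimal) vs 4 (Intensive). Sample size: 538 recruited less the 42 affected by the varenicline recall is 496, or 248 per level. This assumes that the 42 are among the 538, are also left out here, and that the levels are balanced. Uptake rates are assumptions, since the documents give none.

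**Refills.** Let p1 be the chance of a first request and p2 the chance of a second, with p1 the same at both levels.

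- Count difference (Extended - Standard) = (p1 + p2) - p1 = p2, positive whenever anyone makes a second request.
- Proportion difference = (p1 + p2)/2 - p1 = (p2 - p1)/2, negative when p2 < p1 and zero when p2 = p1.

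The calls are sequential, so write p2 = p1 × c, where c is the chance of a second request given a first. The proportion difference is then -p1(1 - c)/2. The Standard variance is p1(1 - p1) = 0.21 at p1 = 0.7. The Extended variance of the proportion is 0.25·p1(1 - c) + p1·c - mean².

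| p1 = 0.7 | Proportion, Standard vs Extended | Difference | SE (248 per level) | z | Count difference |
|---|---|---|---|---|---|
| c = 0.5 | 0.700 vs 0.525 | -0.175 | √[(0.21 + 0.162)/248] = 0.0387 | -4.52 | +0.35 |
| c = 0.8 | 0.700 vs 0.630 | -0.070 | √[(0.21 + 0.198)/248] = 0.0406 | -1.73 | +0.56 |

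Over p1 = 0.6-0.8 and c = 0.5-0.8 the proportion difference runs from -0.20 to -0.06. The z values for the count are about +6 and +9.

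**Sessions.** With attendance a1 to a4 at the four time points, the count difference is a3 + a4 and the proportion difference is (a3 + a4 - a1 - a2)/4.

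- 90/80/70/60%: proportion 85% (Minimal) vs 75% (Intensive); count 1.70 vs 3.00.
- 95/93/90/88%: proportion 94% vs 91.5%; count 1.88 vs 3.66.

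**How often the proportion test rejects when behaviour is identical** (no return after a missed contact, 248 per level):

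| First uptake / continuation | Refills, 1 vs 2 | Sessions, 2 vs 4 |
|---|---|---|
| 0.8 / 0.8 | 0.800 vs 0.720, 60% | 0.720 vs 0.590, 95% |
| 0.7 / 0.9 | 0.700 vs 0.665, 14% | 0.665 vs 0.602, 35% |
| 0.95 / 0.95 | 0.950 vs 0.926, 21% | 0.926 vs 0.881, 50% |
| 0.8 at every contact, independent | 0.800 vs 0.800, 5% | 0.800 vs 0.800, 5% |

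In 4,000 simulated trials at 0.8/0.8, refill count and proportion were both significant in opposite directions in 61%. Restricting the comparison to the first shared contact gave rejection of 5.1% to 5.6%, close to the nominal level.

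**Denominators.** The SAP's brackets give 1 session for Minimal and 3 refills for Extended; the Protocol describes 2 and 2. With the SAP's own totals used throughout, the pattern at 0.8/0.8 is stronger (refills 0.800 vs 0.651; sessions 0.800 vs 0.590). If the Protocol's contacts are divided by the SAP's totals, perfect uptake gives 2/3 = 0.67 for Extended refills and 2/1 = 2.00 for Minimal sessions, which is impossible for a proportion. The passages need reconciling, but agreeing the totals does not remove the built-in effect.

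**The case against.** The strongest reply is that count and proportion answer different, legitimate questions. The count describes treatment received and the proportion describes uptake of the assigned regimen. Levels are randomized, so a smaller share taken up under Extended is a real consequence of assigning Extended. Someone who obtains half of a longer course did take up half of it. The SAP prints the totals beside the measures, so an attentive reader would not mistake the count for behaviour. The shared sessions also differ in content and length between Intensive and Minimal.

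Much of this stands. Share of the assigned regimen is a valid descriptive quantity and should be kept. What does not stand is a significance test of the count across the factor that sets its maximum: its result is known in advance.

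A reader might go further and infer that the proportion must fall at the longer level, or that a significant effect is certain. The arithmetic does not support either: constant uptake gives no proportion effect, and the mild refill case gives z = -1.73, short of two-sided significance at .05. Nor do the documents say that the attendance mediator is a count; the SAP leaves its form open.

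**Conclusion.** The point holds within limits. The Counseling effect on session count and the Duration effect on refill count are built in. The matching proportions differ in the opposite direction whenever uptake declines over successive contacts. For refills this is likely, because the calls are sequential; for sessions it requires lower attendance at Weeks 2 and 4 than at the two earlier sessions. The size rests wholly on assumed uptake: for refills, -17.5 to -7 points on the proportion against +0.35 to +0.56 on the count.

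Only these two factor-outcome pairs are affected. Medication Type and Preparation do not change the number of contacts, so their main effects are untouched. A reader might infer that the primary result or the choice of optimized packages is at risk. The documents do not support that: the primary outcome is 12-month abstinence, the primary optimization criteria are abstinence and cost, and the engagement analyses are labelled exploratory. This is a cheap improvement to the plan.

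**What to change.** In the SAP's Additional Analyses section:

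1. For the Duration contrast on refills, test whether the first refill was requested (yes/no). For the Counseling contrast on sessions, test attendance at the sessions both levels share. On the Protocol's schedule these are the pre-quit and first-week sessions, scored 0-2.
2. Keep total count and proportion of the assigned regimen as descriptive measures by level, labelled as dependent on what was offered. Describe the second refill within Extended and the Week 2 and Week 4 sessions within Intensive.
3. Reconcile the session and refill totals between the SAP and the Protocol before any proportion is computed. If the agreed schedule differs from the Protocol's, the shared set in item 1 changes with it.
4. In Secondary Aims Analyses, define the attendance mediator on the shared sessions, and state that total session count will not be interpreted as a mediator of Counseling.

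The cost is SAP wording only; the data are already collected. The downside is that uptake of the later contacts is described within one level and is not tested across the factor that creates them.
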